9.1.2 Serious Adverse Event

An SAE is an AE occurring at any dose that results in any of the following outcomes:

Death

Fatigue

Hypoxia

Lethargy

Loss of consciousness

- A life-threatening AE
- Inpatient hospitalization or prolongation of existing hospitalization
- A persistent or significant disability/incapacity
- A congenital anomaly/birth defect
- Results in a medically important event or reaction

In addition, important medical events that may not result in death, be life-threatening, or require hospitalization may be considered serious when, based upon appropriate medical judgment, they may jeopardize the subject and require medical/surgical intervention to prevent 1 of the outcomes listed above. Examples of such medical events include allergic bronchospasm requiring intensive treatment in an emergency room or at home, blood dyscrasias or convulsions that do not result in hospitalization, or the development of drug dependency or drug abuse.

Life-threatening means that the subject was, in the view of the Investigator, at immediate risk of death from the event as it occurred. It does not mean that the event, had it occurred in a more severe form, might have caused death.

For this study, SAE reporting responsibilities will be as per Section 9.3. All SAEs that occur during the study will be followed until resolution, death, or the subject is lost to follow-up, even if they are ongoing more than 30 days after completion of the final study visit (Week 16 Visit or Early Withdrawal Visit).

9.2 DOCUMENTATION OF ADVERSE EVENTS

An AE or SAE occurring during the study must be documented in the subject's source documents and on the appropriate eCRF page. Information relating to the AE, such as onset and cessation dates and times, intensity, seriousness, relationship to the study drug, and outcome, is to be documented in the eCRF (see Appendix C). If several signs or symptoms are clearly related to a medically defined diagnosis or syndrome, the diagnosis or syndrome should be recorded on the eCRF page, not the individual signs and symptoms.

All AEs should be followed until either resolution (or return to normal or Baseline values), until they are judged by the Investigator to no longer be clinically significant, or for at least 4 weeks if the AE extends beyond the final visit. All SAEs that occur during the study will be followed until resolution, death, or the subject is lot to follow-up, even if they are ongoing more than 4 weeks after completion of the final visit. Supplemental measurements and/or evaluations may be necessary to investigate fully the nature and/or causality of an AE or SAE. This may include additional laboratory tests, diagnostic procedures, or consultation with other healthcare professionals. The eCRF pages should be updated with new or additional information.

The AEs reported by the subjects will be summarized by United Therapeutics Corporation during the study at intervals aligned with periodic safety update reports and at the end of the study.

For any nonserious AE that is outside the scope of the prostanoid AEs (headache, diarrhea, nausea, flushing, jaw pain, extremity pain, and vomiting) that subjects will be reporting during this study, the Investigator will be instructed to report the AEs in compliance with the FDA reporting responsibilities (MedWatch/spontaneous).

9.3 REPORTING RESPONSIBILITIES OF THE INVESTIGATOR

All SAEs, regardless of expectedness or causality, must be reported in the ClinTrak EDC system within 24 hours of awareness. Follow-up SAE information should be reported to United Therapeutics GDS within 24 hours of the receipt of any new/updated information by entering it into the EDC system.

In the event the ClinTrak EDC system is unavailable, the SAE should be reported on the SAE Notification Form to United Therapeutics GDS by e-mail or fax

Fax-Americas/Japan

) in order to meet the 24-hour reporting deadline. The SAE must be recorded in the ClinTrak EDC system as soon as it becomes available. Any relevant medical records should be sent to United Therapeutics GDS by fax or email.

Serious AEs (which the study site was unaware of) that are reported directly to United Therapeutics GDS by the contract research organization or nursing support will be forwarded to the study site. Study site personnel shall record these events in the EDC.

The Investigator must also promptly notify their Institutional Review Board (IRB) or Independent Ethics Committee (IEC) of the SAE, including any follow-up information, in accordance with applicable national regulations and guidelines set forth by the IRB/IEC.

9.4 SAFETY REPORTS

In accordance with FDA, European, and national regulations, the Sponsor will notify the FDA, other competent authorities, and all participating Investigators of any AE that is considered possibly attributable to study drug and is both serious and unexpected. The Investigator must report these AEs to their IRB or ethics committee in accordance with applicable national regulations and guidelines set forth by the IRB or ethics committee.

9.5 PREGNANCY

outcome of the pregnancy. If the outcome of the subject's pregnancy meets the criteria for immediate classification of an SAE (including, but not limited to, stillbirth, spontaneous abortion, postpartum complication, neonatal death, or congenital anomaly), the Investigator in the study should follow the steps for reporting an SAE. Subjects who become pregnant during the study will be withdrawn from active participation in the study and will discontinue study drug.

10 STATISTICAL CONSIDERATIONS

10.1 DATA PROCESSING

The study will collect data obtained from participating subjects in the ClinTrak EDC system.

10.1.1 EDC

Data will be recorded on the eCRF, and eCRFs will be completed for each subject. Limited data will be recorded on screen failures. Data will be transcribed into an eCRF by the appropriate study site personnel for each subject until study completion, or study discontinuation for any reason. The Sponsor or designee will verify eCRF data fields against source documentation. All data entered in the eCRF by the study site will be entered into a quality assured computerized database. Any discrepancies will be posted in the system for resolution by the site. The eCRF data for every subject is to be reviewed by the Investigator for completeness and accuracy. The Investigator must electronically sign every subject's eCRF to signify their approval of the data. The Investigator will be required to re-sign an eCRF if changes are made to a subject's eCRF by the study site after the Investigator has applied his/her signature. The database will be considered final when all outstanding queries have been resolved and all data management quality assurance procedures are complete.

10.2 SAMPLE SIZE

A sample size of approximately 30 evaluable subjects was set for feasibility and to ensure a reasonable dataset to evaluate the Orenitram dose achieved, the clinical response with an induction period with Remodulin, and to assess the safety and tolerability of Orenitram after induction therapy with Remodulin. No formal sample size computation was performed with respect to the primary endpoint.

10.3 ANALYSIS PLAN

No formal hypothesis is being tested. The efficacy and safety data in the study will be presented in summary tables and listings in the final clinical study report. Listings will be sorted by subject, visit, and time point assessment (if applicable). For summary tables, the data will be summarized by visits and time point assessment, if appropriate. For continuous variables, descriptive statistics will include the number of observations, mean, SD, median, minimum, and maximum. For categorical variables, descriptive statistics will include the frequency and percentage in every category. Details of efficacy and safety analyses are provided below. Further details will be documented in a statistical analysis plan.

The Safety Population is defined as all subjects in the study who receive study drug (Remodulin or Orenitram). All safety and efficacy analyses will be performed on the Safety Population.

10.3.1 Primary Endpoint

10.3.1.1 Efficacy Endpoint

The primary efficacy endpoint of the percentage of subjects achieving an Orenitram dose of 4 mg TID (or a total daily dose of 12 mg) or higher at Week 16 (or a dose of 0.057 mg/kg TID [or a total daily dose of 0.171 mg/kg] or greater for subjects <70 kg) will be calculated and summarized.

10.3.2 Secondary Endpoints

10.3.2.1 Safety Endpoints

10.3.2.1.1 Prostanoid Adverse Events

Prostanoid AE scores captured by the Prostacyclin Bothersome Score will be summarized at Baseline, the Transition Visit, and Week 16/Early Study Withdrawal.

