1.3 RATIONALE FOR DEVELOPMENT OF STUDY DRUG IN DISEASE/CONDITION

Orenitram has demonstrated clinical improvements in exercise capacity after 12 weeks of therapy in subjects with WHO Group I pulmonary hypertension (Jing 2013). It is titrated by 0.25 or 0.5 mg BID or 0.125 mg TID every 3 to 4 days, as tolerated (Orenitram United States Prescribing Information [USPI], 2017). Thus, the maximum doses of Orenitram that can be reached are approximately 1 and 3 mg TID at 1 and 3 months, respectively, which in practice is rarely achieved, often because prostanoid side effects limit aggressive dose titration.

Commercial data demonstrate the median TDD of Orenitram at 6 months is 7.5 mg (Balasubramanian 2017). Results from Orenitram clinical studies show that AEs accounted for approximately 50% of all discontinuations of study drug (Jing 2013, Tapson 2012, Tapson 2013). Anecdotal reports from physicians and nurses suggest that AEs leading to drug discontinuation occur early after starting treatment, and that nausea and vomiting are the most common reasons for drug discontinuation.

Results from a recent clinical study suggest PAH patients previously exposed to Remodulin appear to tolerate significantly higher doses of Orenitram as compared to patients without prior Remodulin exposure (Chakinala 2017). The mean TDD of Orenitram achieved in the pivotal clinical studies was approximately 6 mg at 12 to 16 weeks and 8 mg at 1 year, compared with 40 mg at 24 weeks in the Remodulin to Orenitram transition study (Jing 2013, Tapson 2012, Tapson 2013, Orenitram Package Insert, Chakinala 2017).

Aggressive Remodulin titration can be well-tolerated as demonstrated in multiple prospective studies, with doses ranging from 23 to 139 ng/kg/min at 12 weeks (Sitbon 2007, Hansen 2014, Grünig 2016). This is approximately equivalent to Orenitram 4 to 23 mg TID (TDD of 12 to 70 mg) in a 70-kg patient (Orenitram USPI, 2017). In contrast, commercial data suggest the median TDD of Orenitram at 3 months is 4.5 mg (6.38 mg in transition patients and 4.13 mg in de novo patients taking it TID) (Balasubramanian 2017).

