- If the Investigator deems a subject unsuitable for transition to Orenitram due to significant signs and symptoms of PAH or any other serious safety concerns, the subject may remain on Remodulin for the duration of the study. The Investigator may reverse, or stop the transition to Orenitram due to concerns of subject safety.
- In addition to the scheduled assessments, additional testing will be performed at the Transition Visit as indicated. Subjects may transition at Weeks 2, 4, or 8 if they have achieved a minimum Remodulin dose of 20 ng/kg/min and the Investigator deems the subject suitable for transition. Transition may be reversed or stopped for subject safety.
- t Subjects should be optimized on Remodulin therapy prior to transition to Orenitram; a dose should be achieved that improves the symptoms of PAH while minimizing excessive pharmacologic effects of Remodulin. Transition from Remodulin to Orenitram will occur over the course of 1 to 21 days.

- The study site will contact subjects daily during the first 2 weeks of the study, daily during the transition period (ie, while the subject is on both Remodulin and Orenitram), and twice weekly for the first 2 weeks after transitioning (ie, while the subject is on Orenitram and no longer on Remodulin). At all other time points during the study, subjects will be contacted once weekly.
- The Post Transition Visit occurs 7 to 14 days after transition from Remodulin to Orenitram is initiated. If the Transition Visit occurs at Week 2, the Week 4 visit can be substituted for the Post Transition Visit (ie, an extra visit is not necessary).
- w Study site or pharmacy personnel should assess drug returned and dosing information to confirm drug accountability. See Section 11.5.

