3.6 ESTIMATED STUDY DURATION

The per-subject study period is defined as the date the subject signs the ICF until the Week 16 Visit, the date the subject withdraws from the study, the date a subject dies, or the date a subject is lost to follow-up, whichever occurs first. Subjects who withdraw from study drug prior to Week 16 will be asked to remain in the study up to Week 16 and complete study assessments off treatment.

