7.3.7 Week 16/Early Study Withdrawal (Day 113 [±7 Days])

The following subject-reported data will be completed by the subject at the Week 16/Early Study Withdrawal Visit prior to all other assessments: emPHasis-10 questionnaire and TSQM.

The assessments of Week 16/Early Study Withdrawal Visit can occur over 5 days so that assessments can take place on separate days if needed. All assessments should be conducted prior to withdrawing from the study, prior to discontinuation of Orenitram or Remodulin, and as close as possible to the last dose taken by the subject.

Subjects will return to the study site clinic for the following Investigator-reported assessments:

- PAH symptom score
- · Record of AEs
- AE Bothersome Survey
- ECHO
- WHO FC
- Serum NT-proBNP (samples must be drawn prior to the 6MWT)
- 6MWT (after 10 minutes rest [seated]), immediately followed by heart rate recovery (1 minute) and Borg dyspnea score. If the subject is receiving Orenitram, the 6MWT should occur within 2 to 6 hours of the most recent dose.
- Clinical laboratory assessments
- Vital signs (prior to or at least 30 minutes after the 6MWT, and after 5 minutes rest seated)
- Concomitant medications
- Full physical examination
- Optional biomarker blood sample
- Female subjects of childbearing potential will undergo a urine pregnancy test
- Drug accountability (see Section 11.5)

Subjects who complete the Week 16 Visit will be transitioned off clinical study material to commercially available Orenitram or Remodulin, as clinically appropriate.

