2.3.2 Secondary Endpoints

2.3.2.1 Safety Endpoints

Safety will be assessed using the Prostanoid Adverse Event (AE) scores captured by the AE Bothersome Survey at Baseline, the Transition Visit, and Week 16/Early Study Withdrawal.

The Investigator will administer the AE Bothersome Survey (provided in protocol Appendix E) at time points listed in Table 1 to collect information about prostanoid-related effects experienced by the subject, including headache, diarrhea, nausea, flushing, jaw pain, extremity pain and vomiting. For each prostanoid-related effect, whether the patient has experienced the effect, the degree of bothersome (from 1 - bothers me a lot to 4 - not at all bothersome), and days experiencing it (1 to 7) will be recorded.

Other safety assessments including the incidence of adverse events, clinical laboratory tests, vital signs, and physical examinations are described in Section 3.7.

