3.1.3 Definition of Baseline and transition visit value

Baseline is defined as the last measurement prior to the initiation of Remodulin.

Transition visit value is defined as the last measurement prior to the first dose of Orenitram.

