3.7.1.1 AE Bothersome Survey

Investigators will ask subjects about the prostanoid-related effects they experienced using the AE Bothersome Survey. For this study, adverse events of interest include headache, diarrhea, nausea, flushing, jaw pain, extremity pain, and vomiting. The survey is provided in protocol Appendix E. The number and percentage of subjects reporting each of the adverse events of

interest at Baseline, the Transition Visit, and Week 16/Early Study Withdrawal will be provided (Question 1).

For each symptom (headache, diarrhea, nausea, flushing, jaw pain, extremity pain, and vomiting), AE Bothersome Survey scores will be summarized at Baseline, the Transition Visit, and Week 16/Early Study Withdrawal for each question (Question 2, and Question 3). In addition, change from Baseline and change from Transition Visit will be provided. For each symptom, the following scoring system will be utilized and an overall Burden Score will be provided:

	1 day	2 days	3 days	4 days	5 days	6 days	7 days
Not at all	0	0	0	0	0	0	0
Bothers me a little	3	4	5	6	7	8	9
Bothers me some	5	6	7	8	9	10	11
Bothers me a lot	8	9	10	11	12	13	14

Points	Burden Score
0	Not at all burdensome
3 to 6	Mildly burdensome
7 to 9	Moderately burdensome
10 to 14	Very burdensome

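### For subjects who stay in the study, no AE Bothersome Survey covers at least the first 37 days after a scheduled transition, and its Week 16 summary is not split by current drug, so it cannot isolate Orenitram tolerability

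*Protocol*

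**What the plan says.** The survey is scheduled at three points. Protocol 10.3.2.1.1: "Prostanoid AE scores captured by the Prostacyclin Bothersome Score will be summarized at Baseline, the Transition Visit, and Week 16/Early Study Withdrawal". SAP 3.7.1.1 repeats this: "AE Bothersome Survey scores will be summarized at Baseline, the Transition Visit, and Week 16/Early Study Withdrawal for each question". For each of seven prostanoid effects the subject says whether it occurred in the past week, how bothersome it was, and on how many days (SAP 2.3.2.1: "days experiencing it (1 to 7) will be recorded"). SAP 3.7.1.1 turns bother and days into a Burden Score.

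The middle time point belongs to Remodulin. SAP 3.1.3: "Transition visit value is defined as the last measurement prior to the first dose of Orenitram". The assessment lists for the Post Transition Visit (Protocol 7.3.5) and Week 12 (7.3.6) do not include the survey.

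At Week 16 subjects may be in different treatment states. If judged unsuitable for transition, "the subject may remain on Remodulin for the duration of the study" (Protocol Table 3-1 footnotes). Those who stop study drug early are asked to stay until Week 16 and "complete study assessments off treatment" (Protocol 3.6). SAP 3.7 places all safety summaries in the Safety Population. SAP 3.4 separates Week 16 from early study withdrawal, but only for the efficacy tables.

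**The concern.** Protocol 1.4 hypothesises that Remodulin induction makes Orenitram better tolerated. The survey is the only planned measure of how much prostanoid effects bother the subject and on how many days a week. Protocol 1.3 reports, on anecdotal evidence, that "AEs leading to drug discontinuation occur early after starting treatment", with nausea and vomiting the most common reasons. Both are survey items, yet no survey is scheduled in that period.

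The last column of the table then combines people taking different drugs or none. Protocol 7.3.7 wants the Week 16/Early Study Withdrawal assessments done "prior to discontinuation of Orenitram or Remodulin, and as close as possible to the last dose taken by the subject", but that visit is tied to Week 16 or to leaving the study. When drug is stopped early, Protocol 8.1 asks for the reason, the titration history and any next therapy, not the survey. Someone who stops drug but stays in the study therefore has no survey at stopping, and answers at Week 16 off drug. At stake is whether the change from the Transition Visit to Week 16 can be read as a statement about Orenitram.

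**Working it through.** The documents contain no calculation on this point to reproduce. The check is date arithmetic, followed by a simple mixture.

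**Timing.** Inputs from Protocol 3.1: Week 2 = Day 15 ± 3, Week 4 = Day 29 ± 5, Week 8 = Day 57 ± 5, Week 16 = Day 113 ± 7. Recall is 7 days (Protocol Appendix E).

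- Gap = Week 16 day − Transition Visit day.
- Shortest gap = 106 − latest transition day; longest gap = 120 − earliest transition day.
- Uncovered time = gap − 7.

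| Transition | Gap in days (range) | Uncovered days (range) | Share of gap in recall |
|---|---|---|---|
| Week 2 | 113 − 15 = 98 (88–108) | 91 (81–101) | 7/98 = 7.1% |
| Week 4 | 113 − 29 = 84 (72–96) | 77 (65–89) | 7/84 = 8.3% |
| Week 8 | 113 − 57 = 56 (44–68) | 49 (37–61) | 7/56 = 12.5% |

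The minimum of 37 comes from the latest Week 8 visit (Day 62) and the earliest Week 16 visit (Day 106): 106 − 62 − 7 = 37. Even after a 21-day cross-taper starting at Week 8, the Week 16 survey falls 56 − 21 = 35 days after the cross-taper ends, or 44 − 21 = 23 at the shortest.

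**Mixing.** Pooled rate = (1 − f) × rate on Orenitram + f × rate in the others, where f is the share of others. The documents give no symptom rates, so every rate and count here is an assumption.

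- 30 subjects on Orenitram with 40% reporting nausea (12), plus 5 off drug with none: 12/35 = 34%. Pooling lowers 40% to 34%, about 6 points.
- 30 subjects in all, 5 off drug, 60% on Orenitram: (25 × 0.60 + 5 × 0)/30 = 50%. If 20% of those off drug report the symptom: (15 + 1)/30 = 53%.
- 30 subjects in all, 3 of them early withdrawals or on Remodulin with 90% to 100% reporting: (27 × 0.60 + 3 × 0.90)/30 = 63%, up to (16.2 + 3)/30 = 64%.

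The pooled figure can therefore fall below or rise above the rate in subjects on Orenitram.

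**Effect of two added visits.** With surveys also at the Post Transition Visit and Week 12, the first scheduled reading after starting Orenitram moves from day 56–98 to day 7–14 after the Transition Visit. Three recall weeks would cover 21/98 = 21%, 21/84 = 25% or 21/56 = 37.5% of the gap.

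**The case against.** The strongest reply is that early intolerance is captured elsewhere. SAP 3.7.1 summarises the same seven prostanoid effects, with maximum severity, separately for the Remodulin, Transition and Orenitram phases, and also adverse events leading to Orenitram discontinuation. Protocol 3.3.2.5 has sites contact subjects daily during the cross-taper and twice weekly for the next two weeks. This stands, and it limits the point. It does not close it: severity is the investigator's judgement (Protocol Appendix C), the summary of days at each severity is optional, and neither yields the bother rating or Burden Score. The TSQM side-effect items follow the same three-visit schedule.

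A reader might infer that the survey is never taken early on Orenitram. The documents do not support that. A subject who leaves the study in the first weeks has it at Early Study Withdrawal, and a subject held on Remodulin past Week 8 may transition later (Protocol 6.1), so that the Week 16 survey falls early.

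A reader might also infer a bias toward good tolerability. Off-drug subjects probably lower the rate, but they are not scored as symptom-free by rule; the survey records what they report. Early withdrawals and Remodulin subjects can raise the rate. The off-drug route is also narrow: adding another approved PAH treatment requires withdrawal from the study (Protocol 4.3.1), and an intolerant subject may go back to Remodulin.

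Other qualifications are fair. Subjects reach Orenitram by cross-taper from Remodulin, and titration aims for the maximum tolerated dose by Week 16, so that visit is not inherently a mild one. The survey's stated purpose is prostanoid-related effects in general. The study is uncontrolled and tests no hypothesis, so no schedule would allow a comparison with de novo patients. Visit-level dose listings would let someone rebuild the split by hand, but the planned table does not present it.

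**Conclusion.** The point holds as an inexpensive improvement. For subjects who stay in the study after a scheduled transition, the survey leaves at least 37 days after the Transition Visit uncovered, nominally 49 to 91. Its Week 16/Early Study Withdrawal summary is a mixture that cannot be read as Orenitram tolerability. The primary dose endpoint is unaffected.

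The timing figures rest only on the protocol's visit days, windows and recall period. The effect of mixing cannot be sized from the documents. In the assumed example it is 40% against 34%. A reader might go further, assume that 80% of the five who stopped had nausea at that moment, obtain (12 + 4)/35 = 46%, and read the 12-point difference from 34% as the cost of pooling. That replaces Week 16 answers with assumed answers from an earlier time, so it measures something else.

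**What to change.** In SAP 3.7.1.1:

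- Tabulate the Week 16 survey by drug being taken at the visit (Orenitram, Remodulin, none).
- Show Early Study Withdrawal separately, as SAP 3.4 already does for efficacy.
- Base any statement on Orenitram tolerability on subjects taking Orenitram, together with surveys taken at withdrawal or when Orenitram was stopped.

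This needs no new data, since doses are recorded at study visits on drug (Protocol 3.3.1.1), and it can be done before database lock. The cost is extra columns with small cell counts.

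If subjects are still being followed, also add the survey to the Post Transition Visit (or Week 4 where it substitutes) and to Week 12. Label each survey by the drug or drugs being taken, because the Post Transition Visit can fall within the 1-to-21-day cross-taper. Have subjects who stop study drug but remain in the study complete the survey when they stop, and reconcile Protocol 3.6 with 7.3.7 on this. The cost is a few minutes per visit, about 35 × 2 = 70 extra forms at the two visits, and a protocol amendment with IRB approval. If follow-up is over, state the early gap as a limitation in the study report.

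The instrument should also carry one name: Protocol 10.3.2.1.1 names it differently from Appendix E and the SAP.
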